#### 4.2.5 Antiplatelet Agents and Anticoagulants

Warfarin or vitamin K antagonists should not be administered concomitantly with ibrutinib. Supplements such as fish oil and vitamin E preparations should be avoided. Use ibrutinib with caution in participants requiring other anticoagulants or medications that inhibit platelet function. Participants with congenital bleeding diathesis have not been studied.

For participants requiring the initiation of therapeutic anticoagulation therapy (e.g., atrial fibrillation), consider the risks and benefits of continuing ibrutinib treatment. If therapeutic anticoagulation is clinically indicated, treatment with ibrutinib should be held and not be restarted until the participant is clinically stable and has no signs of bleeding. Participants should be observed closely for signs and symptoms of bleeding. No dose reduction is required when study

drug is restarted.

#### 4.2.6 Surgery

Ibrutinib may increase risk of bleeding with invasive procedures or surgery. The following guidance should be applied to the use of ibrutinib during the perioperative period for participants who require surgical intervention or an invasive procedure while receiving ibrutinib:

- For any surgery or invasive procedure requiring sutures or staples for closure, ibrutinib should be held at least **3 days prior** to the intervention when feasible and should be held at least **3 days after** the procedure and restarted at the discretion of the investigator when the surgical site is reasonably healed without serosanguinous drainage or the need for drainage tubes.
- For minor procedures (such as a central line placement, needle biopsy, lumbar puncture [other than shunt reservoir access], thoracentesis, or paracentesis), ibrutinib should be held for at least **1 days prior** to the procedure when feasible and should not be restarted for at least **1 day after** the procedure. For bone marrow biopsies that are performed while the participant is on ibrutinib, it is not necessary to hold ibrutinib for these procedures.

### 4.3 PROHIBITED CONCOMITANT MEDICATIONS

#### 4.3.1 Prohibited Therapy

Participants who require the use of any of the excluded therapies listed below will be discontinued from study treatment.

Use of the following therapies is prohibited during the study:

- Immunotherapy
- Hormone therapy (other than contraceptives, hormone replacement therapy, or megestrol acetate)
- Any therapies intended for the treatment of lymphoma whether FDA approved or experimental (outside of this study)
- Warfarin or warfarin derivatives

The following concomitant medications are not allowed from 7 days prior to the first dose of study drugs and during study drug administration:

- Strong CYP3A4 inhibitors such as voriconazole, ketoconazole, and clarithromycin
- Strong CYP3A4 inducers such as rifampin and carbamazepine

A comprehensive list of inhibitors, inducers, and substrates may be found at: <https://drug-interactions.medicine.iu.edu/MainTable.aspx>. Pretreatment corticosteroids for CNS disease is permitted before entering this study as explained in Section [2.1.2.4](#).

#### 4.3.2 Vaccines

Live-virus vaccines should not be given at any time during study therapy and are not recommended until B-cell recovery post completion of study therapy.

#### 4.3.2.1 Clarification regarding vaccination against COVID-19:

Vaccines currently authorized or approved for use against COVID-19 in the United States include mRNA vaccines (Pfizer and Moderna vaccines) and a viral vector vaccine (JNJ-78436735 manufactured by Janssen Pharmaceuticals).

In general, it is preferred that participants considering vaccination or booster against COVID-19 complete the vaccination procedures prior to enrollment. Discussion with the Sponsor Medical Monitor to agree upon a safe and appropriate strategy for vaccination of these participants is advised, but not mandatory.

**For participants in the study, vaccination against COVID-19 with a vaccine authorized or approved in the United States is permitted.** Relevant details regarding vaccination will be documented as a concomitant medication and will include the name of the manufacturer of the COVID-19 vaccine. Any adverse events thought to be related to the vaccine will be recorded in the Adverse Event case report form.

## 5 CORRELATIVE STUDIES FOR RESEARCH

### 5.1 BIOSPECIMEN COLLECTION

Sample	Collection Details*	Time Points	Supervising Laboratory/ Investigator ▲
Blood Samples			
ctDNA	• 2 x 10 mL Streck/BCT tube	• Baseline • At the end of every cycle • At follow-up visit (not at 30 Day Safety visit) • At disease progression	BPC
PBMCs for mutational analysis	• 1 x 8 ml CPTs (sodium heparin)	• Baseline • At the end of every cycle • At disease progression	BPC
Cytokines	• 1 x 8-10 mL RTT	• Baseline • End of treatment visit	BPC
Ibrutinib and Venetoclax PK	• 2 x 2ml GTT (sodium heparin)	• C1D1: ➢ Prior to dose of ibrutinib and venetoclax ➢ 1 hour post ibrutinib and venetoclax (+/-20 min) ➢ 10-18 hours post ibrutinib and venetoclax	BPC
CSF*			
ctDNA	• 3 ml in a sterile syringe	• Baseline • At the end of every cycle • At follow-up visit (not at 30 Day Safety visit) • At disease progression	BPC

Sample	Collection Details*	Time Points	Supervising Laboratory/ Investigator ^
Ibrutinib and Venetoclax PK	
 
0.5 mL in a cryovial supplied by Lymphoma Team Research Nurse
 
	
 
C1D1:                     
 
Prior to dose of ibrutinib and venetoclax
 
1 hour post ibrutinib and venetoclax (+/-20 min)
 
10-18 hours post ibrutinib and venetoclax
 
 
 
	BPC
Other samples			
Archival and/or Fresh Tissue Biopsy for gene expression profiling, mutational analysis, and DNA/RNA sequencing.	
 
FFPE (block or slides);
 
Excision (single or multiple nodes) or core (4-6 passes); placed in formalin/FFPE and media, as appropriate
 
	
 
Baseline (optional)
 
At disease progression (optional)
 
	NCI LP/ [name]
Germline DNA for whole exome sequencing	
 
Blood, Buccal swab, or Saliva 1 x 8 ml CPTs (sodium heparin) for blood
 
	
 
Baseline
 
	BPC

\*CSF studies will only be performed in participants with Ommaya Reservoirs.  
 \*\*Tubes/media may be adjusted at the time of collection based upon materials available or to ensure the best samples are collected for planned analyses.  
 ^The location of specimen processing or analysis may be adjusted with the permission of the PI or laboratory investigator.

## 5.2 SAMPLE COLLECTION AND PROCESSING

Any specimens collected on the protocol for specific research analysis that is left over after the analysis is done will be stored for future research.

Note: Platforms and procedures for analysis may be adjusted based upon current technology and/or collaborations in place at the time of actual analysis.

### 5.2.1 Tissue Samples

Tissue samples, both archival and fresh lymph node excision or core needle biopsy samples may be collected as outlined in the table above for research studies, including gene expressing profiling, and mutational analysis.

Archival block(s) or slides (e.g., 15 unstained slides, 5-microns) may be collected, when available from prior or future routine procedures.

Tissue samples will be sent to the Hematopathology Section of Laboratory of Pathology until they are retrieved by staff in the lab of [name], PhD, Lymphoid Malignancies Branch, CCR, NCI.

### 5.2.2 Lymph node excision or core needle biopsy procedure

Participants with accessible tumor tissue who agree to have an optional biopsy performed will be biopsied as outlined in the table in Section 5.1. These samples will be processed as per the standard operating procedures of the Hematopathology Section of the Laboratory of Pathology, NCI, including fresh, frozen and/or formalin-fixed, paraffin-embedded (FFPE) tissue.

If participant has a biopsy during screening to confirm eligibility, baseline biopsy will not be repeated.

Optional tumor biopsies will be obtained by core needle biopsy or surgery. If core biopsies are collected, it is preferable that the interventional radiologist will collect 4-6 core needle biopsies. Biopsies for research will be performed only if there is minimal risk of morbidity. Deep-seated organs such as lung will be excluded from biopsy for research purposes. General anesthesia will not be performed to obtain biopsies for research purposes but when necessary, conscious sedation may be used. If a biopsy is being performed for medical or diagnostic purposes, with or without general anesthesia, a sample may be obtained for research purposes, if adequate tissue is available to meet medical or diagnostic purposes, upon participant consent.

### 5.2.3 Gene expression profiling

Gene expression profiling using Affymetrix U133plus 2.0 arrays will be performed for all cases. For those cases with available fresh frozen pre-treatment biopsy samples, gene expression profiling will be performed as described by the [name] laboratory, with assignment to ABC or GCB subgroups based on a Bayesian predictor. For participants with only an FFPE biopsy sample, we will use a newly described method that can use RNA from FFPE biopsies to accurately predict ABC vs. GCB DLBCL subtypes. Briefly, RNA is extracted from FFPE samples with a Qiagen FFPE extraction kit followed by amplification using uniform and state of the art assay kits, prior to standard Affymetrix U133Plus2.0 array analysis.

### 5.2.4 Mutational analysis

Most primary CNS lymphomas appear to be of non-GCB origin and studies that have looked at mutational analysis of tumors have found a high rate of mutations of the B-cell receptor as well as MYD88 mutations and CARD11 mutations. Therefore, mutational analysis will include but is not restricted to CD79B, CD79A, CARD11 and MYD88, ITAM and A20. This is an evolving field so there may be other mutations and signaling pathways related to NF-kappa B that may also be evaluated. For collection timepoints see table above.

### 5.2.5 Blood and Cerebrospinal Fluid (CSF) Samples

#### 5.2.5.1 Cytokine analysis and circulating tumor DNA (ctDNA)

Cytokine analysis may include but is not limited to the following: IL-6, IL-10, interferon beta, and TNF alpha. Analysis of ctDNA will be performed using blood and CSF samples as described above. CSF studies will only be performed in participants with Ommaya Reservoirs.

### 5.2.5.2 PBMCs for Mutational Analysis

Peripheral blood samples will be sent to Biospecimen Processing Core (BPC) where the samples will be processed to separate out mononuclear cells (PBMC) by Ficoll gradient. The PBMC will be viably frozen and stored in the BPC. Mutational analysis will include but is not restricted to CD79B, CD79A, CARD11 and MYD88, ITAM and A20.

### 5.2.5.3 Pharmacokinetic Analyses of Oral Targeted Therapy (OTT- ibrutinib and venetoclax)

This study provides the opportunity to study the peripheral blood and CSF PK of several anticancer agents. The goal is to have samples of plasma/serum, peripheral blood and CSF PK; CSF PK studies will only be performed in participants with Ommaya Reservoirs.

**NOTE:** Timing of PK sample collection: Every effort will be made to collect samples for PK analysis as prescribed in the table above.

### 5.2.6 Future use of blood, serum, CSF, and tissue specimens

Specimens (blood, serum, CSF, and tissue) collected in the course of this research project will be banked and used in the future to investigate new scientific questions. Future investigations will be conducted on blood, serum, CSF, and tissue specimens and may include analysis of cellular, molecular, genetic and genomic biology and RNA analysis. These studies may involve sequencing of tumor DNA. Samples derived from biopsies may be utilized for procedures such as electron microscopy, immunofluorescence, immunohistochemistry, other histopathologic special stains, establishment of cell cultures, and as a source of material for laboratory studies of nucleic acids and proteins.

## 5.3 SAMPLE STORAGE, TRACKING AND DISPOSITION

### 5.3.1 General

All specimens obtained in the protocol are used as defined in the protocol. Samples from consenting participants will be stored until they are no longer of scientific value or if a participant withdraws consent for their continued use, at which time they will be destroyed.

Samples will be ordered in CRIS and tracked through a Clinical Trial Data Management system. Should a CRIS screen not be available, the CRIS downtime procedures will be followed. Samples will not be sent outside NIH without appropriate approvals and/or agreements, if required.

### 5.3.2 Hematopathology Section of Laboratory of Pathology (Tissue samples)

Archival and/or freshly collected and processed tumor tissue may be stored in the Hematopathology Section of Laboratory of Pathology until ready for planned and/or future research assays if the participant has agreed to allowing specimens to be used in future research studies. IRB approval will be obtained before using any samples to conduct studies that are not described within this protocol. Samples will be stored under conditions appropriate to the type of sample and processing (e.g., ambient or frozen).

Tissue that is given to the technician will be assigned an accession number (HP#) in the HP Case Logbook; sample tracking also takes place with a FileMaker Pro data base called HP Patient Information and Specimen Inventory. A participant background sheet may be filled out and filed with any accompanying paperwork, with final reports and any supplemental reports that follow added as completed.

Archival and/or freshly collected and processed tumor tissue as well as germline DNA samples will be transferred upon request to the [name] lab for sequencing and molecular analysis. These analyses may include, but are not limited to, whole-genome sequencing (WGS), whole-exome sequencing (WES), copy-number alterations (CNA), RNA-sequencing as well as single-cell RNA-sequencing.

#### 5.3.3.1 Sample Data Collection

All samples sent to the Biospecimen Processing Core (BPC) will be barcoded, with data entered and stored in the Labmatrix utilized by the BPC. This is a secure program, with access to Labmatrix limited to defined BPC personnel, who are issued individual user accounts. Installation of Labmatrix is limited to computers specified by the BPC. These computers all have a password restricted login screen.

Labmatrix creates a unique barcode ID for every sample and sample box, which cannot be traced back to participants without Labmatrix access. The data recorded for each sample includes the ID, name, trial name/protocol number, time drawn, cycle time point, dose, material type, as well as box and freezer location. Participant demographics associated with the clinical center participant number are provided in the system. For each sample, there are notes associated with the processing method (delay in sample processing, storage conditions on the ward, etc.).

#### 5.3.3.2 Sample Storage and Destruction

Barcoded samples are stored in barcoded boxes in a locked freezer at either -20 or -80°C according to stability requirements. These freezers are located onsite in the BPC and offsite.

Access to stored clinical samples is restricted. Samples will be stored until requested by a researcher named on the protocol. All requests are monitored and tracked in Labmatrix. All researchers are required to sign a form stating that the samples are only to be used for research purposes associated with this trial (as per the IRB approved protocol) and that any unused samples must be returned to the BPC. It is the responsibility of the NCI Principal Investigator to ensure that the samples requested are being used in a manner consistent with IRB approval.

Sample barcodes are linked to participant demographics and limited clinical information. This information will only be provided to investigators listed on this protocol, via registered use of the Labmatrix. It is critical that the sample remains linked to participant information such as race, age, dates of diagnosis and death, and histological information about the tumor, in order to correlate genotype with these variables.

### 5.3.4 [name] Lab

#### 5.3.4.1 Sample Data Collection

Participant samples, collected for research under this IRB approved protocol, may be archived in the [name] laboratory. All data associated with archived clinical research samples is entered into the web-based NCI Labmatrix database, a centralized system with access controlled via centralized login. Access to this database for samples collected from this study is limited to [name] and his research staff, each requiring individual login and password. All staff in the laboratory receive annually updated NIH/CITI or other training, as appropriate, and maintain standards of computer security.

The data recorded for each sample may include the participant ID, trial name/protocol number, date drawn/collected, treatment cycle/time point, sample source (e.g., peripheral blood, marrow, tissue, etc.) as well as box and freezer location. All received samples will be given a unique bar code number, which will be added to the sample NCI Labmatrix database. Only this bar code will be recorded on the sample vial and the vials will not be traceable back to Participants without authorized access to the NCI Labmatrix database.

#### 5.3.4.2 Sample Storage

Samples are stored in freezers at -80°C (e.g., sera, plasma, tissue samples) or under liquid nitrogen (e.g., cells), according to established stability requirements. These freezers are located onsite under the direction of [name]. Access to samples from this protocol for research purposes will be as outlined in this protocol or by permission of the Principal Investigator only.

### 5.3.5 Study Completion, Future Use and Sample Destruction

The study will remain open so long as sample or data analysis continues. Following completion of the planned analyses, samples will remain in storage as detailed above. Tissue specimens and derived tissue lysates, RNA and DNA collected in the course of this research project may be banked and used in the future to investigate new scientific questions related to this study that are not expressly stated in the present protocol. However, this research may only be done if the proposed research has undergone prospective IRB review and approval, including consent/reconsent if required.

If the participant withdraws consent the participant's data will be excluded from future distributions, but data that have already been distributed for approved research use will not be able to be retrieved.

The PI will record any loss or unanticipated destruction of samples as a deviation. Reporting will be per the requirements of section [7.2](#).

## 5.4 SAMPLES FOR GENETIC/GENOMIC ANALYSIS

#### 5.4.1 Description of the scope of genetic/genomic analysis

The research correlates for this study are expected to include DNA/RNA sequencing of tumors and circulating-tumor DNA (ctDNA). In addition, whole exome sequencing of blood, buccal swab, or saliva may include evaluation for known lymphoma mutations.

#### 5.4.2 Description of how privacy and confidentiality of medical information/biological specimens will be maximized

As stated in section [5.4](#), unique identifiers are attached to samples and are linked through the secure database to medical record information, with the key provided only to researchers on the study. Therefore, potential identification would only occur in the event of a data breach – an unlikely event given the security standards of the databases utilized. A certificate of confidentiality has been obtained (section 13.4). Unlinked genomic data will be deposited in public genomic databases such as dbGaP in compliance with the NIH Genomic Data Sharing Policy ([6.2.2](#)). The pedigree analysis will not be performed.

#### 5.4.3 Management of Results

Participants will be contacted if a clinically actionable gene variant is discovered. Clinically actionable findings for this study are defined as disorders appearing in the American College of Medical Genetics and Genomics recommendations for the return of incidental findings that is current at the time of primary analysis

#### 5.4.4 Genetic Counseling

Participants will be contacted with a request to provide a sample to be sent to a CLIA certified laboratory. If the research findings are verified in the CLIA certified lab, the participant will be offered the opportunity to come to NIH to have genetic education and counseling to explain this result; at the time of any such event(s), these activities will be funded by the NCI/CCR in consideration of the specific circumstances. If the participant does not want to come to NIH, a referral to a local genetic healthcare provider will be provided (at their expense).

This is the only time during the course of the study that incidental findings will be returned. No interrogations regarding clinically actionable findings will be made after the primary analysis.

## 6 DATA COLLECTION AND EVALUATION

### 6.1 DATA COLLECTION

#### 6.1.1 Summary

The PI will be responsible for overseeing entry of data into a data capture system provided by the NCI CCR and ensuring data accuracy, consistency, and timeliness. The principal investigator, associate investigators/research nurses and/or a contracted data manager will assist with the data management efforts. Primary and final analyzed data will have identifiers so that research data can be attributed to an individual human participant.

All adverse events (AEs), including clinically significant abnormal findings on laboratory evaluations, regardless of severity, will be followed until return to baseline or stabilization of event.

Document AEs from the date of first dose of any study drug, through 30 days after the last dose of any study drug. Beyond 30 days after the last intervention, only adverse events which are serious and related to the study intervention need to be recorded

All grade 3, grade 4 and grade 5 abnormal laboratory values will be recorded in the database.

Grade 1 and grade 2 abnormal laboratory values will be recorded in the database as an AE only if

the laboratory abnormality is characterized by any of the following:

- Results in discontinuation from the study
- Is associated with clinical signs or symptoms
- Requires treatment or any other therapeutic intervention
- Is associated with death or another serious adverse event, including hospitalization
- Is judged by the Investigator to be of significant clinical impact
- If any abnormal laboratory result is considered clinically significant, the investigator will provide details about the action taken with respect to the test drug and about the participant's outcome.

The PI (or designee) evaluation of each AE not captured in the clinical database determining that it meets the criteria above will be documented in the source documents.

If any abnormal laboratory result is considered clinically significant, the investigator will provide details about the action taken with respect to the test drug and about the participant's outcome.

Adverse Events of grade 1 will not be collected.

Information on all concomitant medications, administered blood products, as well as interventions occurring during the study must be recorded on the participant's eCRF in C3D

**End of study procedures:** Data will be stored according to HHS, FDA regulations, and NIH Intramural Records Retention Schedule as applicable.

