Grade 3 or 4 nausea, vomiting, or diarrhea if persistent, despite optimal anti-emetic and/or anti-diarrheal therapy	
 
Hold ibrutinib.                             
 
If improves to <math>\leq</math> Grade 2 in <math>\leq</math> 7 days, administer full dose of study treatment for the next cycle.
 
If improves to <math>\leq</math> Grade 2 in > 7 days, reduce the dose of ibrutinib by 1 dose level.
 
 
 
For subsequent episodes, dose reduction 2 of ibrutinib and drug discontinuation will be considered.
 

Grade 3 or 4 atrial fibrillation/flutter or persistent atrial fibrillation/flutter of any grade	
 
Hold ibrutinib.
 
Initiate medical management of atrial fibrillation/flutter.
 
Consider the risks and benefits of restarting ibrutinib treatment. If clinically indicated, the use of anticoagulants or antiplatelet agents may be considered for the thromboprophylaxis of atrial fibrillation.
 

Any other Grade 4 toxicity or unmanageable Grade 3 toxicity attributed to ibrutinib	
 
Hold ibrutinib.                             
 
If improves to < Grade 2 in < 7 days, administer full dose of study treatment for the next cycle.
 
If improves to < Grade 2 in > 7 days, reduce the dose of ibrutinib by 1 dose level.
 
 
 
For subsequent episodes, dose reduction 2 of ibrutinib and drug discontinuation will be considered.
 

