**Table 5: Guidelines for Dose Delay or Modification of Lenalidomide**

Event(s)	Dose Delay or Modification during a cycle
Neutropenia: • Grade 3 (ANC <1,000/ $\mu$ L) for $\geq$ 7 days, OR • Grade 4 (ANC <500/ $\mu$ L) for any duration	

Hold lenalidomide.

Administer growth factors (e.g., G-CSF for neutropenia as indicated).

-If ANC < 1000/<math>\mu</math>L for <math>\leq</math> 7 days, administer full dose of study treatment for the next cycle.

-If ANC < 1000/<math>\mu</math>L for <math>></math> 7 days, reduce the dose of lenalidomide by 1 dose level.

For subsequent episodes, dose reduction 2 of lenalidomide and drug discontinuation will be considered.

If the primary cause of neutropenia is thought to be lymphoma infiltration into the bone marrow, the Principal investigator may elect not to reduce the dose of lenalidomide .

Febrile neutropenia or neutropenia with infection	

Hold lenalidomide until resolution.

Thrombocytopenia: • Grade 3 (decrease to <50,000/ $\mu$ L) associated with > Grade 2 bleeding, OR • Grade 4 (decrease to <25,000/ $\mu$ L) with or without bleeding	

Hold lenalidomide.

-If platelet count < 50,000/<math>\mu</math>L for <math>\leq</math> 7 days, administer full dose of study treatment for the next cycle.

-If platelet count < 50,000/<math>\mu</math>L for <math>></math> 7 days, reduce the dose of lenalidomide by 1 dose level.

For subsequent episodes, dose reduction 2 of lenalidomide and drug discontinuation will be considered.

Grade 1 or 2 neutropenia and/or thrombocytopenia	

No dose reduction or delay.

Rash: • Any Grade desquamating (blistering), OR • Grade 4 non-blistering	

Discontinue lenalidomide.

Thromboembolic event $\geq$ Grade 3	

Hold lenalidomide.

Initiate therapeutic anticoagulation as clinically indicated, please evaluate interactions with other study drugs.

Resume lenalidomide without dose modifications at Day 1 of next cycle if benefit of therapy outweighs bleeding risk.

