  - A FCBP with irregular menstruation must have a pregnancy test weekly for the first 21 days and then every 14 days while on lenalidomide therapy (including breaks in therapy), at discontinuation of lenalidomide and at Day 14 (+/-1 day) and at 30 Day safety visit.
- 24-hour urine creatinine clearance (if needed to measure CrCl in cases where serum creatinine >1.5 mg/dl)
- Urinalysis
- Quantitative Immunoglobulin Panel
- EKG to determine eligibility
- Imaging evaluations:
  - CT scans (chest, abdomen, and pelvis); may be adjusted to assess additional known sites of disease
  - Brain MRI
  - F-FDG-PET Scan brain and body (must be performed at NIH only). Additional PET/MRI may be performed as clinically indicated.

These scans (with the exception of F-FDG-PET) may be performed outside of the NIH and the result forwarded to the study team for review at screening or any time during the study. Given that the methodologies utilized are similar across all facilities, no significant variability is expected and there is no anticipation that study data will be affected.

- Lumbar puncture/Ommaya tap for CSF studies including protein, glucose, cell count/differential, cytology, and flow cytometry to determine eligibility and during the study if clinically indicated.
- Bone marrow aspiration/biopsy should be performed within 3 months prior to starting protocol treatment. May be repeated after Cycle 6 if the previous test result was positive or if otherwise clinically indicated.
- Study drug administration schedule- see Section [3.2](#)
- Adverse events and concomitant medication review: Adverse events and concomitant medication will be continuously monitored throughout the study until disease progression

or end of treatment visit. Adverse events that occur beyond 30 days after the last administration will be recorded per [6.1](#).

- Correlative studies: Refer to section [5](#)

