#### 10.4.4 Safety Analyses

The safety of the agents will be reported by tabulating the number of participants who experience toxicity, by grade and type of toxicity.

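### Section 6.1.1 excludes all Grade 1 adverse events, so the safety data can omit the reason a study drug was held or stopped under the any-grade rules in Tables 3 and 5

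*Combined protocol and SAP*

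**What the plan says.** Section 6.1.1 makes three statements that bear on Grade 1 events.

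- All adverse events, "regardless of severity, will be followed until return to baseline or stabilization of event".
- For laboratory findings, "Grade 1 and grade 2 abnormal laboratory values will be recorded in the database as an AE only if" a listed criterion is met. The criteria include "Results in discontinuation from the study", associated signs or symptoms, a need for treatment, and investigator judgement of significant clinical impact.
- Without any exception, "Adverse Events of grade 1 will not be collected".

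Two dose-modification rules act on non-laboratory events regardless of grade. Table 5 (Section 3.3.4) discontinues lenalidomide for a rash described as "Any Grade desquamating (blistering), OR" Grade 4 without blistering. Table 3 (Section 3.3.3) holds ibrutinib for Grade 3 or 4 atrial fibrillation or flutter, and also for "persistent atrial fibrillation/flutter of any grade".

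Section 10.4.4 reports safety by "tabulating the number of participants who experience toxicity, by grade and type of toxicity". Section 10.4.8 plans no tabulation of individual participant data.

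**The concern.** The Grade 1 sentence in 6.1.1 cannot be applied literally alongside the laboratory exception in the same section: a Grade 1 laboratory abnormality that meets a criterion is to be recorded as an adverse event, and Grade 1 adverse events are not to be collected. A data manager has to guess that the exception prevails.

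The larger gap is outside the laboratory. The protocol treats two clinical events as important enough to hold or stop a drug at any grade, but the data rule has no matching exception. A participant could have lenalidomide stopped, or ibrutinib held, for an event that never enters the adverse event data. The planned safety output is a table by grade and type, with no individual listing beside it, so nothing in the analysis plan would show the omission. Safety and tolerability are the primary objective, and the reasons drugs were held or stopped are part of that description.

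**Working it through.** **1. The plan's own figures.** Section 10.2 gives n = 10, a threshold of 7 successes, and success rates of 50% and 80%.

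- P(X ≥ 7 | n = 10, p = 0.50) = (120 + 45 + 10 + 1)/1024 = 176/1024 = 0.1719, stated as 17.2%.
- P(X ≥ 7 | n = 10, p = 0.80) = 0.8791, stated as 87.9%.

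Both reproduce. Neither depends on which grades of adverse event are collected.

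**2. Is a Grade 1 event behind a hold or stop recorded?** Taking the routes into the data in turn:

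| Type of Grade 1 event | Rule | Recorded? |
|---|---|---|
| Laboratory abnormality meeting a 6.1.1 criterion | 6.1.1 exception, against the Grade 1 exclusion in 6.1.1 | Contradictory as written |
| Serious event | 8.2: SAEs captured in the clinical database, no grade limit | Yes |
| Event of special interest | 8.1.6 and 8.3: expedited report on the SAE form | Reported, no grade limit |
| Non-serious, non-laboratory event leading to a drug hold or stop | 6.1.1 exclusion only | Not required |

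The last row is the gap. The laboratory criteria do not close it: they apply to laboratory values, and the nearest one concerns leaving the study, not holding or stopping one drug.

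**3. Which any-grade rules fall in that row?** Two: blistering rash (lenalidomide discontinued, Table 5) and persistent atrial fibrillation or flutter (ibrutinib held, Table 3).

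**4. Does the gap reach the primary endpoint?** Section 10.4.2 counts a participant as a success after at least 2 cycles without having to discontinue treatment for toxicity. A hold is not a discontinuation. Under Section 3.3.1, stopping one drug leaves the participant on the others; two or more must be stopped before treatment ends. The definition has no grade threshold, and no document derives the count from the adverse event table. What can be lost is the recorded cause, not the count.

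**5. Size.** The documents give no rate for Grade 1 blistering rash or Grade 1 persistent atrial fibrillation, so the expected number of omitted events cannot be calculated. The effect of one event depends on the denominator: 1/10 = 10% of the primary-endpoint set, 1/14 = 7.1% of those 10 plus the four Arm 1 participants, and 1/16 = 6.3% at the accrual ceiling if all 16 are treated. Sections 10.2 and 10.3.1 make all treated participants evaluable for toxicity, so the 10% figure does not describe the toxicity population as a whole.

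**The case against.** Several points on the other side stand.

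- Collecting mainly Grade 2 and above is a legitimate choice. The statement about following all events whatever their severity concerns clinical follow-up, not database entry, so it does not itself contradict the Grade 1 exclusion.
- Serious events are already captured at any grade, events of special interest are reported on the SAE form, and concomitant medications and interventions go on the eCRF.
- Section 6.4 grades events by CTCAE v5.0, which the documents do not reproduce. Whether a blistering rash, or persistent atrial fibrillation needing medical management, can be Grade 1 cannot be settled from the documents. The point takes 'any grade' at face value.

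None of this removes the conflict over Grade 1 laboratory events, or supplies a rule for a non-serious clinical event behind a drug hold or stop.

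Two stronger readings are tempting, and the documents do not support them. A reader might infer that the safety tables would hide the cause of a primary-endpoint failure. That would need a second drug to be stopped, another ground for removal under Section 3.8.1, or a reading of discontinuing treatment in Section 10.4.2 as stopping any single drug. The plan does not define it that way, and Section 3.3.1 keeps the participant on treatment after one drug is stopped.

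A reader might also infer that the capture window is stated inconsistently and drops events after progression, because Section 3.4.2 has events "continuously monitored throughout the study until disease progression" or the end-of-treatment visit. But the next sentence there refers to 6.1 for events beyond 30 days after the last administration. Appendix D schedules adverse event assessment at progression and at Day 30, and Section 3.8 seeks a 30-day safety visit for all participants. The Appendix D footnotes on assessment through follow-up are compatible with 6.1.1, which continues to record serious related events after 30 days.

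**Conclusion.** A cheap improvement, not a threat to the trial's conclusion. As written, the Grade 1 exclusion in 6.1.1 conflicts with the laboratory exception beside it, and has no counterpart to the any-grade rules in Tables 3 and 5. Following it literally can leave the reason for a drug hold or stop out of the adverse event data and the 10.4.4 table.

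This rests on two assumptions: that such an event can be Grade 1, and that it is not serious, since a serious event would be captured under Section 8.2. The number of such events is unknown. The success count and the operating characteristics of the 7-of-10 rule do not change.

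**What to change.** In Section 6.1.1, replace the Grade 1 sentence with a rule of this form: Grade 1 AEs are entered only when they lead to a hold, reduction or discontinuation of any study drug, are serious or AESI, or meet the laboratory criteria listed above; each is entered with its grade and the action taken.

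In Section 10.4.4, add a table footnote saying that Grade 1 events are selectively captured, so that the Grade 1 counts are not read as incidence.

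Optionally, have Section 3.4.2 and the Appendix D footnotes cross-refer to the full 6.1.1 window. Keep the provision for serious related events beyond 30 days; a bare 30-day limit would remove it.

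The cost is a few lines of text and a small amount of extra data entry in a study of at most 16 participants. No dose, clinical rule, sample size or decision threshold changes.
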